- Collect a blood sample for immunogenicity testing.
- If the participant is part of the group for description of cell-mediated immune response (select sites only), collect a blood sample (approximately 120 mL) for PBMC isolation.

- Ask the participant to contact the site staff or investigator if a medically attended event (eg, doctor's visit, emergency room visit) or hospitalization occurs.
- Ask the participant to contact the site staff or investigator (this could be via the COVID-19 illness e-diary) immediately if the participant experiences any respiratory symptoms as detailed in Section 10.10.8.6.4.1.
- Ensure the participant has a self-swab kit.
- Schedule an appointment for the participant to return for the next study visit.
- Complete the source documents.

10.10.8.6.3.8. Visit 508 – 6-Month Follow-Up Visit (After Vaccination 3) (175 to 189 Days After Visit 506)

- Collect a blood sample for immunogenicity testing.
- If the participant is part of the group for description of cell-mediated immune response (select sites only), collect a blood sample (approximately 120 mL) for PBMC isolation.
- Record details of any of the prohibited medications specified in Section 6.8.1 received by the participant if required for his or her clinical care.
- For participants who are HIV-positive, record the latest CD4 count and HIV viral load.
- Collect the participant's e-diary or assist the participant to remove the study application from his or her own personal device.
- Complete the source documents.
- The investigator or an authorized designee completes the CRFs.
- Record any AEs that occur within the 48 hours after the blood draw as described in Section 8.3.

10.10.8.6.4. COVID-19 Surveillance (All Substudy D Participants)

If a participant experiences any of the following (irrespective of perceived etiology or clinical significance), he or she is instructed to contact the site immediately and, if confirmed, participate in an in-person or telehealth visit as soon as possible, optimally within 3 days of symptom onset (and at the latest 4 days after symptom resolution).

- A diagnosis of COVID-19;
- Fever;
- New or increased cough;

- New or increased shortness of breath;
- Chills;
- New or increased muscle pain;
- New loss of taste/smell;
- Sore throat;
- Diarrhea;
- Vomiting.

Note that:

- If new symptoms are reported within 4 days after resolution of all previous symptoms, they will be considered as part of a single illness and a second illness visit is not required;
- Surveillance of potential COVID-19 symptoms should continue even if a participant has a positive SARS-CoV-2 test earlier in the study.

During the 7 days following each vaccination, potential COVID-19 symptoms that overlap with specific systemic events (ie, fever, chills, new or increased muscle pain, diarrhea, vomiting) should not trigger a potential COVID-19 illness visit unless, in the investigator's opinion, the clinical picture is more indicative of a possible COVID-19 illness than vaccine reactogenicity. If, in the investigator's opinion, the symptoms are considered more likely to be vaccine reactogenicity, but a participant is required to demonstrate that he or she is SARS-CoV-2—negative, a local SARS-CoV-2 test may be performed: if positive, the symptoms should be recorded as a potential COVID-19 illness; if not, the symptoms should be recorded as AEs.

Participants may utilize a COVID-19 illness e-diary through an application (see Section 10.10.8.6.5) installed on a provisioned device or on the participant's own personal device to prompt him/her to report any symptoms. Note that this does not substitute for a participant's routine medical care. Therefore, participants should be encouraged to seek care, if appropriate, from their usual provider.

10.10.8.6.4.1. Potential COVID-19 Illness Visit (Optimally Within 3 Days After Potential COVID-19 Illness Onset)

This visit may be conducted as an in-person or telehealth visit; a telehealth visit involves the sharing of healthcare information and services via telecommunication technologies (eg, audio, video, video-conferencing software) remotely, thus allowing the participant and investigator to communicate on aspects of clinical care.

As a participant's COVID-19 illness may evolve over time, several contacts may be required to:

- Record AEs, as appropriate as described in Section 8.3. Note: Potential COVID-19 illnesses that are consistent with the clinical endpoint definition should not be recorded as AEs. These data will be captured as efficacy assessment data only on the relevant pages of the CRF, as these are expected endpoints.
- Record details of any of the prohibited medications specified in Section 6.8 received by the participant if required for his or her clinical care.
- If the visit is conducted in person, obtain a nasal (midturbinate) swab (collected by site staff). Alternatively, if the visit is conducted by telehealth, instruct the participant to self-collect a nasal (midturbinate) swab and ship for assessment at the central laboratory.
- Collect COVID-19—related standard-of-care clinical and laboratory information. This includes, but is not limited to:
 - Symptoms and signs, including
 - Clinical signs at rest indicative of severe systemic illness (RR ≥30 breaths per minute, HR ≥125 beats per minute, SpO₂ ≤93% on room air at sea level, or PaO₂/FiO₂ <300 mm Hg)
 - Evidence of shock (SBP <90 mm Hg, DBP <60 mm Hg, or requiring vasopressors)
 - Significant acute renal, hepatic, or neurologic dysfunction
 - Respiratory failure (defined as needing high-flow oxygen, noninvasive ventilation, mechanical ventilation, or ECMO)
 - Clinical diagnosis
 - Local laboratory SARS-CoV-2 test result(s). Note that if it is routine practice to perform a repeat local SARS-CoV-2 test for any reason, then a repeat nasal (midturbinate) swab should also be obtained and shipped for assessment at the central laboratory.

- Full blood count
- Blood chemistry, specifically creatinine, urea, LFTs, and C-reactive protein
- Imaging results (eg, CT or MRI scan) to document neurologic dysfunction
- Number and type of any healthcare contact; duration of hospitalization and ICU stay
- Death
- Complete the source documents.
- The investigator or an authorized designee completes the CRFs.

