10.10.3. Objectives, Estimands, and Endpoints

| Objectives | Estimands | Endpoints |
|---|---|--|
| | Primary Safety | |
| To describe the safety and tolerability profile of BNT162b2 OMI given as the third, fourth, or fifth dose to BNT162b2-experienced participants, or as a 2-dose series to COVID-19 vaccine—naïve participants To describe the safety and tolerability profile of BNT162b2 given as a third or fourth dose to BNT162b2-experienced participants (Group 2b, Group 4, and Group 5) | In participants receiving at least 1 dose of study intervention, the percentage of participants reporting: Local reactions for up to 7 days following each dose Systemic events for up to 7 days following each dose AEs from the first study vaccination (received in this study) through 1 month after the last study vaccination SAEs from the first study vaccination (received in this study) through 6 months after the last study vaccination | Local reactions (pain at the injection site, redness, and swelling) Systemic events (fever, fatigue, headache, chills, vomiting, diarrhea, new or worsened muscle pain, and new or worsened joint pain) AEs SAEs |
| | Primary Immunogenicity BNT162b2-experienced participants | |
| G1vG2bA: To descriptively compare the anti-Omicron immune response after 1 dose of BNT162b2 OMI to after 1 dose of BNT162b2 given as the third dose in BNT162b2-experienced participants | In participants complying with the key protocol criteria (evaluable participants) and with evidence of past SARS-CoV-2 infection: • GMR of the Omicron-neutralizing titers at 1 month after 1 dose of BNT162b2 OMI to those at 1 month after 1 dose of BNT162b2 given as the third dose in BNT162b2-experienced participants • The difference in percentages of participants with seroresponse to the Omicron strain at 1 month after 1 dose of BNT162b2 OMI and at 1 month after 1 dose of BNT162b2 given as the third dose in BNT162b2-experienced participants | SARS-CoV-2 Omicron-neutralizing titers |

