- If the participant is part of the group for description of cell-mediated immune response (select sites only), collect a blood sample (approximately 120 mL) for PBMC isolation and a further blood sample (approximately 5 mL) for HLA typing.
- Obtain a nasal (midturbinate) swab (collected by site staff).

As Cohort 1 is observer-blinded, the blinded and unblinded roles should still be maintained to ensure the integrity of the blind:

- Blinded site staff will obtain the participant's randomization number using the IRT system. The randomization confirmation report with the study intervention allocation will only be sent to the unblinded site staff member.
- Unblinded site staff member(s) will dispense/administer 1 dose of study intervention into the deltoid muscle of the preferably nondominant arm. Please refer to the IP manual for further instruction on this process.
- Blinded site staff must observe the participant for at least 30 minutes after study intervention administration for any acute reactions. Record any acute reactions (including time of onset) in the participant's source documents and on the AE page of the CRF, and on an SAE form as applicable.
- Provide a measuring device to measure local reactions at the injection site and a thermometer for recording daily temperatures and fever (COVID-19 surveillance) and provide instructions on their use.
- Explain the e-diary technologies available for this study (see Section 8.2.4), and assist the participant in downloading the study application onto the participant's own device or issue a provisioned device if required.
- Provide instructions on reactogenicity e-diary completion and ask the participant to complete the reactogenicity e-diary from Day 1 through Day 7, with Day 1 being the day of vaccination.
- Provide instructions on COVID-19 illness e-diary completion and ask the participant to
 complete the COVID-19 illness e-diary if the participant is diagnosed with COVID-19 or
 has possible new or increased symptoms, and when he/she receives a reminder, at least
 weekly. See Section 10.10.8.6.4 for further details. Provide a self-swab kit in case of
 COVID-19 symptoms and provide instructions on self-collection of nasal swabs.
- Ask the participant to contact the site staff or investigator immediately if the participant experiences any of the following from Day 1 through Day 7 after vaccination (where Day 1 is the day of vaccination) to determine if an unscheduled reactogenicity visit is required:

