10.10.8.6.8. Unscheduled Visit for a Grade 3 or Suspected Grade 4 Reaction

If a Grade 3 local reaction (Section 8.2.4.2), systemic event (Section 8.2.4.3), or fever (Section 8.2.4.4) is reported in the reactogenicity e-diary, a telephone contact should occur to ascertain further details and determine whether a site visit is clinically indicated. If suspected Grade 4 local reaction (Section 8.2.4.2), systemic event (Section 8.2.4.3), or fever (Section 8.2.4.4) is reported in the reactogenicity e-diary, a telephone contact or site visit should occur to confirm whether the event meets the criteria for Grade 4.

A site visit must be scheduled as soon as possible to assess the participant unless any of the following is true:

- The participant is unable to attend the unscheduled visit.
- The local reaction/systemic event is no longer present at the time of the telephone contact.
- The participant recorded an incorrect value in the reactogenicity e-diary (confirmation of a reactogenicity e-diary data entry error).
- The PI or authorized designee determined it was not needed.

This telephone contact will be recorded in the participant's source documentation and the CRF.

If the participant is unable to attend the unscheduled visit, or the PI or authorized designee determined that it was not needed, any ongoing local reactions/systemic events must be assessed at the next study visit.

During the unscheduled visit, the reactions should be assessed by the investigator or a medically qualified member of the study staff such as a study physician or a study nurse, as applicable to the investigator's local practice, who will:

- Measure body temperature (${}^{\circ}F/{}^{\circ}C$).
- Measure minimum and maximum diameters of redness (if present).
- Measure minimum and maximum diameters of swelling (if present).
- Assess injection site pain (if present) in accordance with the grades provided in Section 8.2.4.2.
- Assess systemic events (if present) in accordance with the grades provided in Section 8.2.4.3.
- Assess for other findings associated with the reaction and record on the AE page of the CRF, if appropriate.

The investigator or an authorized designee will complete the unscheduled visit assessment page of the CRF.

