10.10.9.3.2. Primary Endpoint(s)/Estimand(s) Analysis

| Endpoint | Statistical Analysis Methods |
|----------------|--|
| Safety | • Descriptive statistics will be provided for each reactogenicity endpoint for each vaccine group. Local reactions and systemic events from Day 1 through Day 7 after each study vaccination (where Day 1 is the day of vaccination) will be presented by severity and cumulatively across severity levels. Descriptive summary statistics will include counts and percentages of participants with the indicated endpoint and the associated Clopper-Pearson 95% CIs. |
| | AEs and SAEs will be categorized according to MedDRA terms. Counts, percentages, and associated Clopper-Pearson 95% CIs of AEs within 1 month and SAEs within 6 months after the last study vaccination will be provided for each vaccine group. |
| Immunogenicity | For each primary immunogenicity estimand described in Section 10.10.3 |
| | • GMRs and the associated 2-sided 95% CIs will be calculated using the method described in Section 9.3.1.2.3. |
| | • The percentages of participants with seroresponse for each group will be provided. The difference in percentages of participants with seroresponse and the associated 2-sided 95% CIs will be calculated using the Miettinen and Nurminen method (see Section 9.3.1.1). |
| | • For Cohort 1, only participants with evidence of past SARS-CoV-2 infection will be included in the analysis. For Cohort 2, only participants with no serological or virological evidence (up to 1 month after receipt of 1 dose of study intervention) of past SARS-CoV-2 infection will be included in the analysis. |
| | • For Cohort 2 and Cohort 3, superiority based on GMR will be established if the lower bound of the 2-sided 95% CI for the GMR is >1; noninferiority based on seroresponse rate difference will be established if the lower bound of the 2-sided 95% CI for the difference in percentage is greater than -5%. |

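### In Substudies D, E and F, a solicited reaction already covered by the e-diary is also recorded as an AE if an optional local SARS-CoV-2 test is not positive, so one reaction can count in two primary safety endpoints

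*Protocol*

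**What the plan says.** Protocol Section 10.10.8.6.4 (Substudy D) deals with COVID-19 symptoms in the 7 days after each vaccination that coincide with solicited systemic events: "ie, fever, chills, new or increased muscle pain, diarrhea, vomiting". If the investigator thinks reactogenicity the likelier cause but the participant has to show a negative status, "a local SARS-CoV-2 test may be performed". The result decides the record: "if positive, the symptoms should be recorded as a potential COVID-19 illness; if not, the symptoms should be recorded as AEs". Sections 10.11.8.6.8 (Substudy E) and 10.12.8.5.6 (Substudy F) carry the same rule.

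The vaccination-visit text, for example in Section 10.10.8.6.1.1, asks every participant to "complete the reactogenicity e-diary from Day 1 through Day 7, with Day 1 being the day of vaccination". Section 10.10.3 lists two separate primary safety endpoints that matter here:

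- "Systemic events (fever, fatigue, headache, chills, vomiting, diarrhea, new or worsened muscle pain, and new or worsened joint pain"), collected for up to 7 days after each dose;
- "AEs from the first study vaccination (received in this study) through 1 month after the last study vaccination".

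Sections 10.11.3 and 10.12.3 set up the same pair for the single dose in Substudies E and F. Under Section 10.10.9.3.2, "Descriptive statistics will be provided for each reactogenicity endpoint for each vaccine group", and AE percentages are tabulated separately by vaccine group.

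**The concern.** A solicited reaction is meant to be measured by the e-diary, in the same way for everyone. This rule sends some of those reactions to the AE page as well. What selects them is an outside requirement for a test, such as an employer's, and not severity, seriousness or duration.

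Take two participants with the same fever and chills on Day 2, both judged to be reactogenicity. The first needs no test: the reaction is a systemic event, and this rule does not send it to the AE page. The second needs a test, which is not positive: the same reaction is a systemic event and is recorded as an AE too. The second participant now counts in the AE percentage, although the two reactions were identical.

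At stake is the meaning of a primary safety endpoint. The AE percentage through 1 month becomes a mixture of other adverse events and a test-selected share of solicited reactions. In Substudies E and F the internal review of sentinel participants also looks at AEs and e-diary data side by side through Day 7 (Sections 10.11.9.4.2 and 10.12.9.4.2), where the same reaction could appear twice.

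**Working it through.** The protocol states no figure on this point, so the main check compares the texts.

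**1. Symptoms.** The rule covers five: fever, chills, muscle pain, diarrhea and vomiting. All five are in the systemic-event endpoint of Section 10.10.3 and its counterparts in 10.11.3 and 10.12.3.

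**2. Time.** The rule applies to the 7 days after vaccination, and the e-diary runs from Day 1 to Day 7. The AE endpoint runs from vaccination through 1 month, so it contains the e-diary period.

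**3. Exclusion.** Nothing in the available text removes these events from either endpoint.

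**4. Neighbouring rules.** Section 10.10.8.6.4.1 keeps illnesses that meet the COVID-19 endpoint definition off the AE record, which prevents double capture in that direction. At the unscheduled reactogenicity visit, Section 10.10.8.6.8 reserves the AE page for something other than the graded reactions: "Assess for other findings associated with the reaction and record on the AE page of the CRF, if appropriate". The surveillance rule has no comparable safeguard.

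**5. Result.** A tested reaction can count in both endpoints. An identical untested one is not sent to the AE page by this rule.

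**Illustration of size.** The protocol gives no symptom, testing or background AE rates by arm. Every input here is an assumption:

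- *b* = 5%, AE rate without the rule
- *s* = 30% or 50%, participants with an overlapping symptom
- *t* = 2%, 10% or 30%, symptomatic participants who are tested locally
- *n* = 95%, tests that are not positive
- other AEs occur independently of symptoms and testing

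AE percentage with the rule = *b* + (1 − *b*) × *s* × *t* × *n*.

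Example with *s* = 30%, *t* = 10%: 0.05 + 0.95 × 0.30 × 0.10 × 0.95 = 0.0771, or 7.71%.

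| Tested (*t*) | AE % if *s* = 30% | AE % if *s* = 50% | Difference (points) |
|---|---|---|---|
| 2% | 5.54 | 5.90 | 0.36 |
| 10% | 7.71 | 9.51 | 1.80 |
| 30% | 13.12 | 18.54 | 5.42 |

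With *s* = 30% in both arms the difference is 0.0 points, but each arm's AE percentage still rises by 0.5 points (5.54 − 5) to 8.1 points (13.12 − 5). The table shows how the mechanism works and how strongly it depends on *t*. It does not estimate anything in this trial.

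**The case against.** The strongest objection is that only half of the protocol is available. AE recording is referred to Section 8.3 and e-diary reactions to Section 8.2.4, and neither can be read here. The amendment history (Section 10.13, Amendment 4) indicates that Section 8.2.4.2 does govern when a reaction is also an AE, since a Grade 4 reaction is to be reported as one. Acute reactions in the 30 minutes after injection also go to the AE page on an e-diary day. Some dual recording is therefore deliberate, and a reader who inferred that any overlap between e-diary and AE page is an error would go too far. This part stands and limits the fix. It does not remove the point: the surveillance rule is an explicit instruction to sites, and a general rule elsewhere that kept e-diary events off the AE page would contradict it and still need reconciling.

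A reader might also infer that the more reactogenic arm is bound to collect more AEs. The protocol does not establish that. In Substudy D both vaccines are given at 30 µg (Section 10.10.6). In Substudies E and F the 30 µg versus 60 µg comparison makes a difference plausible, and Sections 10.11.2.2 and 10.12.2.2 report more severe systemic reactions with ascending dose, but for a related candidate (BNT162b1). Participants and safety evaluators in E and F are blinded, so nothing suggests that testing given symptoms depends on arm. The imbalance remains a conditional inference.

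The trigger is also narrow, since the participant must need a negative status and the test is optional; the effect may be small. Safety is summarised descriptively, with no composite of the two endpoints, and AEs are tabulated by MedDRA term, so a reader can see fever or chills listed. All of this stands and bears on the size. How AE tables handle overlapping events could be left to the SAP, but the site instruction that creates the overlap is in the protocol.

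**Conclusion.** The point holds in limited form. As written in all three substudies, the rule lets one solicited reaction count in two primary safety endpoints, and makes its AE status depend on an optional local test. The effect is an upward shift in a descriptive AE percentage. Its size cannot be estimated from the protocol; on the assumed inputs above it runs from 0.5 points (5.54 − 5) to 13.5 points (18.54 − 5) within an arm.

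A difference between arms with the same number of doses and the same testing practice arises only if their reactogenicity differs. That is most plausible in Substudies E and F and is not shown for Substudy D. The documents do not support reading this as a demonstrated bias between arms, or as an error in any hypothesis test.

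The conclusion assumes that Sections 8.2.4 and 8.3 contain no specific exception for these events. It is worth correcting because the wording is an active instruction to sites and the remedy is short.

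**What to change.** **Protocol text.** In Sections 10.10.8.6.4, 10.11.8.6.8 and 10.12.8.5.6, append to the sentence quoted above the words *unless already captured in the reactogenicity e-diary*. State that this does not override other AE and SAE reporting requirements in Sections 8.2.4 and 8.3, for example for Grade 4 reactions and SAEs.

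**Data already collected.** Keep every AE the investigator recorded. Flag AEs with onset on Day 1 to Day 7 that match an e-diary systemic event of the same participant and date, and show the AE summary with and without the flagged events. Deleting them by programmed matching is not advisable: it would discard investigator-recorded events from a primary safety table and could only lower the rate, and a fever with a negative SARS-CoV-2 test may be another illness.

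**Cost.** One clause in three sections, a small matching step in programming, and one additional table. No new data are needed.
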